7.1.4.1 Adverse Events of Special Interest

Adverse events of special interest (AESIs) are not assessed during the study.

7.1.5 Methods for Recording Adverse Events and Serious Adverse Events

All findings in subjects experiencing SAEs and any medication or other therapeutic measures used to treat the SAE in addition to the outcome of the SAE after PCEC rabies booster dose or collected during physical exams at Scheduled and Ad hoc visits, must be reported both on the VSAE Report Form which is part of the Investigator Site File and in the eCRF.

Investigator must report those events to his/her corresponding EC or applicable regulatory authorities in accordance with institutional policy/regulatory requirements and adequate documentation of this notification must be provided to the Sponsor. During the course of the study, all SAEs which occur from the time of booster administration until completion of safety follow-up period (the day of the next Scheduled Clinic Visit after booster vaccination or on the date of Early Termination Visit, whichever is earlier), whether considered to be associated with the study vaccination or not, must be reported within 24 hours of the site becoming aware of the event to GSK or its designee. Specific instructions and contact details for collecting and reporting SAEs to GSK will be provided to the investigator.

After receipt of the initial report, representatives of GSK or its designee will contact the investigator if it is necessary to obtain further information for assessment of the event.

GSK or its designee must also comply with the applicable regulatory requirement(s) related to the reporting of suspected unexpected serious adverse vaccine reactions (also known as SUSARs) to the regulatory authorities and the IRB/EC. If a SUSAR or other safety signal relating to use of one of the study vaccines is reported to GSK or its designee, the Sponsor will communicate the information to the investigator and the investigator will be responsible for submitting this information to the EC and other relevant authorities.

All SAEs will be evaluated by the investigator for relationship of the event to study vaccine. SAEs that are judged to be possibly or probably related to the study vaccine should be reported to the Sponsor as related/suspected events, *irrespective of time frame of SAEs reporting.*

The relationship of the study vaccine to a SAE will be determined by the investigator based on the following definitions:

1. Related/suspected

The SAE is judged by the investigator to be possibly or probably related to the study vaccine on the AE CRF page (see [section 7.1.3, Evaluation of Adverse Events](#)).

2. Not Related

The SAE is not related if exposure to the study vaccine has not occurred, **or** the occurrence of the SAE is not reasonably related in time, **or** the SAE is considered unlikely to be related to use of the study vaccine, i.e., there are no facts (evidence) or arguments to suggest a causal relationship.

In addition, SAEs will be evaluated by the Sponsor or designee for “expectedness.” An unexpected AE is one that is not listed in the current SmPC or an event that is by nature more specific or more severe than a listed event.

In addition, a pre-existing event or condition that results in hospitalization should be recorded on the Medical History CRF.

If the onset of an event occurred before the subject entered the study (e.g., any pre-planned hospitalization for conditions like cosmetic treatments or for non-emergency routine visits for a pre-existing condition), the hospitalization would not lead to an AE being classified as serious.

If the investigator judges that the hospitalization was prolonged as a result of the event itself or was necessary due to a worsening of the pre-existing condition, the hospitalization would then be considered as a SAE.

Additionally, the investigator will evaluate whether the SAEs lead to withdrawal of subject from the study.

All SAEs will be monitored until resolution or until the investigator assesses them as chronic or stable. All subjects experiencing SAEs from the time the subject receives the booster dose until he or she completes the specified safety follow-up period (i.e. the day of next Scheduled Clinic Visit after booster vaccination **or on the date of Early Termination Visit, whichever is earlier**) - whether considered associated with the use of the study vaccine or not - must be monitored until symptoms subside and any abnormal laboratory values have returned to baseline, or until there is a satisfactory explanation for the changes observed, or until death, in which case a full pathologist’s report should be supplied, if possible. The investigator’s assessment of ongoing SAEs at the time of each subject’s last visit should be documented in the subject’s source document.

7.1.5.1 Post-Study Events

Any SAE that occurs outside of the protocol-specified *safety* follow-up period (*after Study Termination Visit or Early Termination Visit whichever is earlier*) and *the investigator considers* to be caused by the study vaccine must be reported to GSK or its designee.

7.1.6 Pregnancies

To ensure subjects' safety, *all pregnancies* must be reported to GSK or delegate *within 2 weeks of site becoming aware of a pregnancy*. If the subject agrees to submit this information, the pregnancy must be followed to determine outcome, including spontaneous or voluntary termination, details of the birth, and the presence or absence of any birth defects, congenital abnormalities, or maternal and/or newborn complications. This follow-up should occur even if intended duration of safety follow-up for the study has ended.

Pregnancy data must be recorded on a Pregnancy Report CRF (initial report) and Pregnancy Follow-Up CRF (outcome report) and reported to GSK or delegate. Instructions and contact details for submitting the Pregnancy CRFs will be provided to the investigator.

Any pregnancy outcome meeting the definition of SAEs (see section 7.1.4, Serious Adverse Events) reported in subjects who received booster administration needs to be reported within 24 hours of the site becoming aware of the event to GSK or delegate using the VSAE Report Form and be recorded in the CRF(s).

The Pregnancy Form must also be updated for further internal processing.

Any pregnancy outcome meeting the definition of SAEs reported in subjects who have NOT received booster administration need to be reported within 24 hours of the site becoming aware of the event to GSK or delegate using the VSAE Report Form, although such SAEs will not be a part of the Clinical database and do not need to be recorded in the CRF(s).

The Pregnancy Form must also be updated for further internal processing.

7.1.7 Safety Laboratory Measurements

This study has no safety laboratory measurements.

7.2 Efficacy Assessment

This study has no efficacy measurements.

7.3 Immunogenicity Assessment

The measures of immunogenicity used in this study are standard, i.e., widely used and generally recognized as reliable, accurate, and relevant (able to describe the quality and extent of the immune response).

- Protection against rabies is dependent on the presence of RVNA. WHO recommended method to measure RVNA serum concentrations is RFFIT. A neutralizing antibody titer of ≥ 0.5 IU/mL is regarded by the WHO as being an ‘adequate’ antibody response following rabies vaccination, and is used as a threshold in clinical trials.
- Blood samples from all subjects at Scheduled Clinic Visits 1 through 8 (Year 3 through Year 10), and, only from those subjects who received booster vaccination, also at Additional Clinic Visits 1.2 through 7.2, will be used for serology analysis. Refer to [section 3.0, Study Design](#).
- Testing will be conducted by a GSK or designated, qualified laboratory in a blinded manner towards the treatment arm. Refer to the Protocol Ancillary Document for names and details.

8.0 STATISTICAL CONSIDERATIONS

8.1 Endpoints

8.1.1 Primary Endpoint(s)

8.1.1.1 Primary Safety Endpoint(s) (Amended 25 February 2019)

For subjects receiving PCEC rabies booster vaccination, SAEs and the associated concomitant medications will be collected starting from the time of booster administration until *completion of safety follow-up period (the day of the next Scheduled Clinic Visit after booster vaccination or on the date of Early Termination Visit, whichever is earlier)*.

8.1.1.2 Primary Efficacy Endpoint(s)

Not applicable.

8.1.1.3 Primary Immunogenicity Endpoint(s) (Amended 25 February 2019)

- Time to first RVNA concentrations <0.5 IU/mL.
- **Geometric Mean Antibody Concentrations (GMCs)** and **Geometric Mean ratio (GMRs)** for subjects receiving the booster dose, as measured by antibody concentration at 7 days after the booster dose vs. antibody concentration before the booster dose.
- Percentages of subjects with RVNA concentrations ≥ 0.5 IU/mL, as measured by RFFIT assay at 7 days after the booster dose and at Year 3, 4, 5, 6, 7, 8, 9 and 10 Scheduled Clinic Visits.

8.1.2 Secondary Endpoint(s)

8.1.2.1 Secondary Safety Endpoint(s)

Not applicable.

8.1.2.2 Secondary Efficacy Endpoint(s)

Not applicable.

8.1.2.3 Secondary Immunogenicity Endpoint(s) (Amended 25 February 2019)

- GMCs at Year 3, 4, 5, 6, 7, 8, 9 and 10;

- Reverse Cumulative Distribution Plots (RCDPs) at Year 3, 4, 5, 6, 7, 8, 9 and 10;
- Percentages of subjects with RVNA concentrations ≥ 0.5 IU/mL, as measured by RFFIT assay at Year 3, 4, 5, 6, 7, 8, 9 and 10.

8.1.3 Exploratory Endpoint(s)

8.1.3.1 Exploratory Safety Endpoint(s)

Not applicable.

8.1.3.2 Exploratory Efficacy Endpoint(s)

Not applicable.

8.1.3.3 Exploratory Immunogenicity Endpoint(s)

Not applicable.

8.2 Success Criteria

8.2.1 Success Criteria for Primary Objective(s)

Not applicable.

8.2.1.1 Success Criteria for Primary Safety Objective(s)

Not applicable.

8.2.1.2 Success Criteria for Primary Efficacy Objective(s)

Not applicable.

8.2.1.3 Success Criteria for Primary Immunogenicity Objective(s)

Not applicable.

8.2.2 Success Criteria for Secondary Objective(s)

8.2.2.1 Success Criteria for Secondary Safety Objective(s)

Not applicable.

8.2.2.2 Success Criteria for Secondary Efficacy Objective(s)

Not applicable.

8.2.2.3 Success Criteria for Secondary Immunogenicity Objective(s)

Not applicable.

8.3 Analysis Sets

8.3.1 All Enrolled Set

All screened subjects who provide informed consent and provide demographic and/or baseline screening assessments.

8.3.2 All Exposed Set

All subjects in the enrolled set who receive a booster dose.

8.3.3 Safety Set

Safety Set

All subjects in the Exposed Set with unsolicited adverse event data.

Overall Safety Set

Not applicable.

8.3.4 Full Analysis Set (FAS) Immunogenicity Set

Full Analysis Set Immunogenicity

Time to first RVNA concentrations <0.5 IU/mL.

All subjects in the All Enrolled Set who provide immunogenicity data until first time RVNA concentration is <0.5 IU/mL.

GMR for subjects receiving the booster dose, as measured by antibody concentration at 7 days after the booster dose vs. antibody concentration before the booster dose.

All subjects in the All Enrolled Set who provide immunogenicity data after booster dose.

Percentages of subjects with RVNA concentrations ≥ 0.5 IU/mL, as measured by RFFIT assay at 7 days after the booster dose and at Year 3, 4, 5, 6, 7, 8, 9 and 10 Scheduled Clinic Visits.

All subjects in the All Enrolled Set who provide immunogenicity data after booster dose.

GMCs, percentages and RCDPs of subjects with RVNA concentrations ≥ 0.5 IU/mL, as measured by RFFIT assay at Year 3, 4, 5, 6, 7, 8, 9 and 10.

All subjects in the All Enrolled Set who provide immunogenicity data at relative time-points. After having received the booster dose, subjects will not be included in these analyses any longer.

Further details on Full Analysis Immunogenicity sets are provided in the statistical analysis plan.

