8.4.3.3.3 Statistical Methods

Geometric Mean Concentration (GMC).

RVNA GMCs will be based on the logarithmically transformed (base10) values.

GMCs with the associated 95% confidence intervals (CIs) will be computed for each vaccine group at Year 3, 4, 5, 6, 7, 8, 9 and 10 by taking the exponential of the corresponding log-transformed (least squares) means and 95% confidence intervals, from an ANOVA model with fixed factors for group and center. Group differences along with

95%CIs will also be computed. Subjects will be included in this analysis until they receive the booster dose and they will be excluded thereafter.

Reverse Cumulative Distribution Plots.

The reverse cumulative distribution plots will be provided at Year 3, 4, 5, 6, 7, 8, 9 and 10 by treatment group.

Percentages of subjects with RVNA concentrations ≥ 0.5 IU/mL.

As a form of supplementary information, also percentage of subjects with RVNA concentrations ≥ 0.5 IU/mL, as measured by RFFIT assay at Year 3, 4, 5, 6, 7, 8, 9 and 10 will be presented in a tabular fashion.

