7.3. Full Analysis Set (FAS), Immunogenicity

FAS-1: Booster immunogenicity analysis

All subjects in the Enrolled Set who receive at least one booster dose during the trial (because RVNA value below 0.5 IU/mL at scheduled visit) or before entering the trial (e.g. travellers to endemic areas or veterinarians who got the booster regardless of the RVNA value) and provide immunogenicity data.

FAS-2: Long term immunogenicity analysis

All subjects in the Enrolled Set who provide immunogenicity data.

Note: In the long-term immunogenicity analysis, when a subject receives a rabies vaccine booster dose (before or during the study) because RVNA value is below 0.5 IU/mL, subsequent RVNA values after the booster dose will be set to half of the detection level (i.e. 0.1 IU/mL) until study end even if the subject withdraws earlier than last study visit (see last part of section [8.2](#) for a detailed explanation).

In case a subject receives a booster dose before or after entering the study (e.g. travellers to endemic areas, veterinarians) but the last known RVNA value was above 0.5 IU/mL, then he/she will be excluded from the long term immunogenicity analysis set (i.e. FAS-2 and PPS). This is justified by the fact that including actual values as recorded after the booster dose would inflate the immunogenicity persistence; on the other hand, it would be inappropriate to apply the same rule used for subjects receiving a booster dose when RVNA value is less than 0.5 IU/mL as this is not the case.

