8.2. Handling of Dropouts, Missing Data

Time to event analysis:

The Cox proportional hazards regression model analysis will be based on methods for right-censored data ([Lindsey](#), 1998).

In this setting, the event/failure will be represented by having a RVNA concentration <0.5 IU/mL (see section [8.8](#)). Subjects without event (with missing blood draw, or lost to follow up or early terminated) will be regarded as right-censored data.

GMC and percentage analysis - boostability:

To evaluate the booster response in terms of Geometric Mean Concentration (GMC), Geometric Mean Ratio (GMR) and percentage of subjects with RVNA concentration ≥ 0.5 IU/mL; missing data will be not included in the analysis.

GMC and percentages of subjects with RVNA concentrations ≥ 0.5 IU/mL

To evaluate the long-term (up to approx.10 years) immunogenicity in subjects who received a primary series of accelerated or conventional rabies PrEP in the parent study (V49_23) in terms of GMC and percentage of subjects with RVNA concentration ≥ 0.5 IU/mL; missing data as such will be not included in the analysis. If a subject receives a rabies vaccine booster dose, the RVNA value after booster will be set to half of quantification level from that moment onward. This because the exposure to a booster dose during the trial introduces a bias, as the RVNA concentrations will reflect the booster response and not the long-term persistence after the primary series (i.e., vaccination received at time of parent study).

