All further subject immunogenicity data will not be used for Time to event analysis.

GMC and percentage analysis - boostability:

Subject is included in the Exposed to Booster Set and independently on time or visit in which booster is administered the time-points will be as following:

- Pre-booster
- 7 days after booster
- 6 to 9 months after booster

Long-term persistence of antibody responses after primary series

All immunogenicity data until booster will be part of analysis as they are reported.

For subjects receiving a booster dose, the following method of imputation will be used for antibody values:

- Values, missing or not, will be replaced with half of the quantification level (0.1 IU/mL) from that moment onward.

Subjects receiving a booster dose outside of the study and for which RVNA value at the time of booster vaccination is not available will be excluded from FAS-2 and PPS-2 (see section 7.3 for details)

Duration in the Study

Duration in the study is defined in days as:

Last visit date (visit x)^a – Enrollment date (visit 1) + 1

^a or premature discontinuation date (in case of withdrawal from the study)

The duration is missing if one of the dates is missing or incomplete.

Unsolicited Serious Adverse Events

All serious adverse events (AEs) following *Rabipur* booster dose within the study will be characterized according to the date of occurrence related to the vaccination phase as follows:

- **Emergence before vaccination phase:** start date before the first date of injection of study vaccine.
- **Emergence during vaccination phase:** start date on or after the first date of injection of study vaccine or, adverse event increase in severity including to “serious” AE.

If start date is equal to the first date of injection then “timing” variable (“On injection day, before injection”/“On injection day, after injection”) will be used to define whether the adverse event occur before or after the injection.

If an AE start date is missing or unknown, the AE will be considered as emergent.

When start and/or end dates of an AE are only partially known, AEs will be categorized as emergent before, during, or after vaccination phase using the following rules:

- If the partial end date is before ($<$) the first study vaccination (i.e., year or year & month is/are before the first study vaccination year or year & month) then the AE is emergent before vaccination phase.

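### Protocol and SAP treat boosted subjects in opposite ways in the secondary yearly summaries, and the protocol's removal rule selects on the outcome

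*Protocol*

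**What the plan says.** **Protocol.** Section 8.3.4 defines the analysis set for GMCs, percentages and RCD plots at Years 3 to 10, and ends: "After having received the booster dose, subjects will not be included in these analyses any longer". Section 8.4.3.3.3 computes each year's GMCs "from an ANOVA model with fixed factors for group and center" and adds: "Subjects will be included in this analysis until they receive the booster dose and they will be excluded thereafter". The synopsis has the same sentence.

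The rule belongs to the secondary yearly summaries only. For the primary-endpoint percentages (Day 7 after booster and the Scheduled Visits), 8.3.4 uses a different set: "All subjects in the All Enrolled Set who provide immunogenicity data after booster dose". The section closes with "Further details on Full Analysis Immunogenicity sets are provided in the statistical analysis plan".

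**SAP.** For subjects boosted because RVNA was below 0.5, section 7.3 says "subsequent RVNA values after the booster dose will be set to half of the detection level", to study end and even after withdrawal. Section 8.2 says "the RVNA value after booster will be set to half of quantification level from that moment onward", and section 8.8 says "Values, missing or not, will be replaced with half of the quantification level (0.1 IU/mL) from that moment onward". Section 11.3 applies this to the secondary long-term analysis, including the RCD figure, and replaces the yearly ANOVA with a mixed model for repeated measures.

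**Dates.** The current protocol is Amendment 2 (25 February 2019). The SAP history lists the imputation and the mixed model under June 2019 without saying that they depart from the protocol. The February 2022 SAP amendment still cites Protocol Amendment 2.

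**The concern.** Two current documents give incompatible rules for the same secondary endpoints, so a reader of the protocol would expect different numbers from those the SAP will produce.

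The protocol rule also has a statistical fault. The in-study booster is given only when RVNA falls below 0.5 IU/mL, so the endpoint itself triggers removal. After Year 3, the percentage at or above 0.5 describes only those not yet boosted. It approximates one minus that year's rate of new drops, not the share of the original cohort still protected. SAP 11.2 says that the regimens already differed in persistence at Day 366, so the faster-waning group would lose its low values sooner and the groups would look more alike.

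The secondary objective is immunogenicity to about 10 years. Protocol 8.6 and SAP 14.1 allow the Year 6 interim report to go to a health authority.

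**Working it through.** **Inputs.** From the documents: eight yearly visits (Years 3 to 10), booster threshold 0.5 IU/mL, SAP imputed value 0.1 IU/mL. They give no waning rate, SD, effect size or dropout rate, and there is no stated figure to reproduce. All rates below are assumptions. *No boosting* means the value that would be seen if nobody were boosted.

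**1. Closed form.** Assume everyone below 0.5 is boosted and a constant share *h* newly falls below 0.5 at each visit, Year 3 included. At visit *k*:

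- protocol percentage = 1 − *h*
- SAP percentage = (1 − *h*)^*k*

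At Year 10, *k* = 8:

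| *h* | Protocol | SAP |
|---|---|---|
| 2% | 98% | 85% |
| 3% | 97% | 78% |
| 5% | 95% | 66% |
| 8% | 92% | 51% |

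For two regimens with *h* = 5% and 10%, the protocol gap is 95 − 90 = 5 points at every visit. The SAP gap is:

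- Year 3: 95 − 90 = 5 points; share hidden by the protocol rule 0%
- Year 4: 90.25 − 81 = 9.25 points; hidden 1 − 5/9.25 = 46%
- Year 10: 66.3 − 43.0 = 23.3 points; hidden 1 − 5/23.3 = 79%

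**2. Simulation, 400,000 subjects per scenario.** Log10 RVNA falls 0.05 a year on average, with SD 0.40 (intercept), 0.04 a year (slope) and 0.15 (assay). Everyone below 0.5 is boosted. Year 10 results, as percentage at or above 0.5 and GMC (IU/mL):

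| Year 3 mean log10 | Protocol | SAP | No boosting |
|---|---|---|---|
| 0.35 | 93.4%, 1.70 | 65.3%, 0.73 | 72.3%, 1.00 |
| 0.7 | 96.7%, 2.76 | 87.2%, 1.99 | 89.9%, 2.24 |
| 0.2 | 92.0%, 1.47 | 53.0%, 0.47 | 61.7%, 0.71 |

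- Percentage gap between the last two rows: 4.7 points (protocol), 34.2 (SAP), 28.2 (no boosting). Hidden against no boosting: 1 − 4.7/28.2 = 83%.
- Log10 GMC ratio: log10(1.47/2.76) = −0.27 (protocol), log10(0.71/2.24) = −0.50 (no boosting). Hidden: 1 − 0.27/0.50, about 45%.
- In the 0.2 group the protocol percentage rises from 88.0% at Year 3 to 92.0% at Year 10, while the no-boosting value falls from 88.0% to 61.7%.

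**3. Range.** Nine decay scenarios: Year 3 GMC 1.0–8 IU/mL, yearly fall 0.01–0.12 log10, between-subject SD 0.25–0.45, noise 0.05–0.15. Each was run with full booster uptake and no dropout, and with 80% uptake and 5% yearly dropout.

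- Percentages: 44–93% of the no-boosting Year 10 gap was hidden, and at least half in all but one scenario.
- GMCs: 10–63% of the no-boosting log ratio was hidden.

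**4. A limiting case.** With late, fast waning (Year 3 mean 0.7, fall 0.12 a year, SDs 0.25, 0.02 and 0.15), the protocol percentage falls from 100% to 82.5% and the no-boosting value to 69.0%. Hidden waning is (31.0 − 17.5)/31.0, about 44%. The GMC falls from 5.01 to 0.91 (protocol) against 0.72 (no boosting), so about 12% of the log decline is hidden.

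**5. Source of the GMC bias.** One mid-range scenario, 1,500 per arm, with Year 3 GMCs of 2.41 and 1.22:

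| Method | Year 10 GMC, conventional / accelerated |
|---|---|
| Full data, no boosting | 1.23 / 0.65 |
| Drop boosted, yearly ANOVA (protocol) | 1.94 / 1.40 |
| Drop boosted, random-intercept mixed model | 1.26 / 0.67 |
| SAP imputation at 0.1, mixed model | 0.92 / 0.41 |

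The third row is close to the first because the low value that triggers removal stays in the model. The bias comes from removal combined with a separate ANOVA each year.

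**The case against.** The strongest reply is that the SAP is later, that the protocol defers to it, and that it already retains boosted subjects and uses a repeated-measures model. If the SAP is followed, the report will not carry the protocol's bias. That largely stands, and it lowers the urgency. It does not remove the conflict: the protocol defers further details of the sets, and reversing an explicit exclusion is more than a detail.

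The affected analyses are secondary, there is no hypothesis or success criterion, and cumulative persistence is the first primary endpoint. The Kaplan-Meier and Cox analyses do not use the removal rule. All of this stands.

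Removal follows receipt of a booster, not a low result. Subjects below 0.5 who miss the Ad hoc Visit, are pregnant (protocol 3.8) or fail the pre-booster criteria (4.2) stay in. One minus the drop rate is therefore exact only with full uptake, and the remaining set is *not yet boosted*, not *never below 0.5*.

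A reader might infer that the protocol rule hides most of the waning and most of any regimen difference. The documents give no rates to support that. It often fails for GMCs, and it fails for the percentages under late, fast waning.

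**Conclusion.** The contradiction is a matter of text and is certain. The direction of the protocol rule's bias is also clear: later-year percentages and RCD curves at 0.5 overstate persistence and understate regimen differences. The size rests on assumed decay rates: often about half or more of the Year 10 percentage gap, and a smaller, variable share for GMCs (about 10–63% of the log ratio). Year 3 is essentially unaffected, and the primary time-to-event comparison is not affected.

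The SAP rule should not be taken as the unbiased reference. It overstates waning relative to no boosting (65.3% against 72.3% in the first simulated row). With 80% uptake and 5% yearly dropout the mid-range conventional group gave 70.1% against 80.0%, because boosted dropouts stay as failures while unboosted dropouts leave.

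This should be fixed, but it is an unreconciled protocol rather than a bias that the report is bound to carry.

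**What to change.** Amend protocol 8.3.4, 8.4.3.3.3 and the synopsis, and align SAP 7.3, 8.2, 8.8 and 11.3, so that both documents state one estimand:

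- **Yearly percentages, and RCD curves at 0.5.** Keep a subject boosted for RVNA below 0.5 in the denominator and count them as below 0.5 at later Scheduled Visits. Describe this as persistence without yet having been boosted for RVNA below 0.5, and say that it lies below the value expected had nobody been boosted.
- **Yearly GMCs.** Replace the per-visit ANOVA with the repeated-measures model on all pre-booster Scheduled Visit values. Do not enter post-booster values as observed. Run the SAP's 0.1 IU/mL imputation as a sensitivity analysis. SAP 8.1 and 11.3 name only Visits 1 to 7 for this model, so Visit 8 must be added to reach Year 10.
- **Any summary that drops boosted subjects.** Label it *among subjects not yet boosted*.

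The cost is wording and some programming, with no new data. The downside is that reported persistence will look less favourable than under the protocol rule.
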